8.5. Study size

Sample size calculations are not applicable as this is a descriptive study. The expected number of patients eligible for the study is about 500-700 patients.

8.6. Data management

Part of the data will be collected from the main database, such as demographics, comorbidities, systemic therapy (not including chemotherapy like cisplatin or carboplatin), date of death. Data that is not available in the main database such as tumor characteristics (stage of disease, histology), chemotherapy (cisplatin, carboplatin), response (from imaging results), biomarker status, metastases site, Eastern Cooperative Oncology Group (ECOG) results, and discontinuation will be extracted through additional chart review from medical letters in PDF format by trained data extractors. Extracted data will be recorded in an electronic case report form created for this study using Microsoft Access Database. All data is anonymous and does not leave the MHS system.

SPSS version 24 and R data processing and statistical software will be used.

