8. RESEARCH METHODS

8.1. Study design

This is a population based retrospective database study that will include patients with metastatic, HR+/ HER2- breast cancer and who initiated first or subsequent lines of treatment with palbociclib. Data will be available from Maccabi Healthcare Services (MHS) database in Israel for patients who received approval for treatment with palbociclib since 01 January 2018 until 31 August 2020.

Treatment amendment and extension: Treatment lines will be rerun for the same patient cohort for an additional year and a half of follow-up to 30 June 2022.

The database review followed by a medical record review will capture data from approximately 500-700 patients on demographics, clinical characteristics, disease history, treatment history, palbociclib dosing, clinical outcomes and post-palbociclib combination therapy treatment data. The study will be descriptive in nature therefore no control or comparator groups will be included.

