8.3. Variables

The following variables will be collected from the MHS electronic database and non-structured data extracted from PDF files of patient data:

Variable	Source	Role in study	Period of measurement	Reporting phase	Operational definition
Demographic and Clinical and health related characteristics at baseline					
PatID	MHS structured data	Data linkage		Not reported	Unique patient identifier used to link clinical records. This information will not be disclosed to the study sponsor.
Gender	MHS structured data	Baseline characteristic	Prior medical history	Reported	Male/Female
Age	MHS structured data	Baseline characteristic	Baseline	Reported	Patient's age (in years) at index date.
Age groups	MHS structured data	Baseline characteristic	Baseline	Reported	Groups such as <50 versus ≥ 50
Body mass index (BMI)	MHS structured data	Baseline characteristic	Baseline	Reported	Median (Interquartile Range - IQR)
BMI groups	MHS structured data	Baseline characteristic	Baseline	Reported	Underweight (BMI < 18.5), normal (BMI 18.5-24.9), overweight (BMI 25-25.9), obese (BMI ≥ 30), missing
Smoking history	MHS structured data	Baseline characteristic	Baseline	Reported	Ever smoker, never smoker, unknown.

Menopausal status	MHS structured data	Baseline characteristic	Baseline	Reported	Pre-, peri- or post-menopausal
Region of residence	MHS structured data	Baseline characteristic	Baseline	Reported	North, South, Central region
Socioeconomic status	MHS structured data	Baseline characteristic	Baseline	Reported	Based on a points system, categorized as low (1-4), medium (5-6), high (7-10)
Co-morbidities	MHS validated registries	Baseline characteristic	Baseline	Reported	For cardiovascular disease, cerebrovascular disease, stroke, congestive heart failure, diabetes mellitus, chronic kidney disease, hypertension, Chronic obstructive pulmonary disease (COPD).
Variable	Source	Role in study	Period of measurement	Reporting phase	Operational definition
Chronic diseases	MHS structured data	Baseline characteristic	Baseline	Reported	Depression as defined by ICD-9 codes.
Deyo-Charlson Comorbidity index	MHS structured data and MHS validated registries	Baseline characteristic	Baseline	Reported	
Co-medications	MHS structured data	Baseline characteristic	Baseline	Reported	At least 2 purchases within 3 months prior to index date.
Genetic counselling for gBRCAm (germline Breast Cancer gene mutation)	MHS structured data	Baseline characteristic	Baseline	Reported	yes/no

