Genetic testing for gBRCAm performed	MHS structured data	Baseline characteristic	Baseline	Reported	yes/no
Death	MHS structured data	Endpoint	After index date		Death is captured from National Insurance Data
Disease Characteristics					
Date of initial breast cancer diagnosis	National cancer registry	Baseline characteristic	Baseline	Reported	Records may be incomplete
Histology	Extracted from PDF patient data files	Baseline characteristic	Baseline	Reported	
Location of metastases	Extracted from PDF patient data files	Baseline characteristic	Baseline	Reported	Bone, brain, lymph nodes, ovary, visceral
Visceral/non visceral status	Extracted from PDF patient data files	Baseline characteristic	Baseline	Reported	Non-visceral, visceral (lungs, liver), bone only
Eastern Cooperative Oncology Group (ECOG) performance status at diagnosis	Extracted from PDF patient data files	Baseline characteristic	Baseline	Reported	Grouped as 0-1, 2, 3-4, unknown/missing
Molecular status data: performed HER2/ HR tests	Extracted from PDF patient data files	Baseline characteristic	Baseline	Reported	yes/no
Hormone sensitivity	Extracted from PDF patient data files	Baseline characteristic	Baseline	Reported	primary or secondary resistance
Variable	Source	Role in study	Period of measurement	Reporting phase	Operational definition
Progression of disease from imaging	Extracted from PDF patient data files	Baseline characteristic	Baseline	Reported	
Treatment Characteristics					

Index treatment regimen	MHS structured data	Treatment characteristic	Study observation period	Reported	Palbociclib combination treatment - combination with aromatase inhibitor or fulvestrant.
Lines of therapy	MHS structured data and PDF patient data files.	Treatment characteristic	Study observation period	Reported	Identified according to the sequence of dispensed medications.
Median duration of each line of therapy	MHS structured data	Treatment characteristic	Study observation period	Reported	Duration in weeks or months between the start and stop of each line of therapy will be reported as mean (SD) and median (IQR)
Number of cycles of index treatment	MHS structured data	Treatment characteristic	Study observation period	Reported	Mean (SD) and Median (IQR)
Index palbociclib treatment dose	MHS structured data	Treatment characteristic	Study observation period	Reported	Mean (SD) and Median (IQR)

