Index palbociclib treatment dose schedule change	MHS structured data	Treatment characteristic	Study observation period	Reported	Proportion of patients with dose changes
Date of treatment initiation	MHS structured data	Treatment characteristic	Study observation period	Not Reported	First date will be used if a regimen consists of more than one drug given on different dates.
Index treatment end date	MHS structured data	Treatment characteristic	Study observation period	Not Reported	Date of final treatment for each drug or regimen. It is possible that the patient's treatment stop date is not documented if the patient dies, is lost to follow up or is still on therapy. The final treatment date death date or end of

					study date will be used, whichever is earliest.
Variable	Source	Role in study	Period of measurement	Reporting phase	Operational definition
Post-palbociclib treatment duration	MHS structured data	Clinical Outcomes	Study observation period	Not Reported	
The regimen received by patients following discontinuation from the palbociclib treatment.
 
The duration (in weeks) between the start and stop of the post-palbociclib treatment. Findings will be summarized as the mean (\pm SD) and median (range) of values.

					subsequent treatment for unknown reasons
Time to chemotherapy after palbociclib treatment	MHS structured data	Clinical Outcomes	Study observation period	Reported	Time to chemotherapy (Kaplan Meier method median (95% CI)) from end of index treatment and start of chemotherapy. Summary of number of events and censored patients at 6, 12, 18, 24 months.
Time to next treatment (TTNT)	MHS structured data	Treatment characteristic	Study observation period	Reported	TTNT will be defined as the interval (in weeks or months) between the start of the index treatment date and the date of the next-line treatment. Patients who did not advance to the next treatment will be censored on the study end date or death, whichever occurs first. Kaplan-Meier (K-M) method with 95% CI and summary tables of

					events and censored patients at 6, 12, 18, 24 months.
CCI					

8.3.1. Demographic characteristics at baseline (from structured electronic database):

- Patient demographics: age, age group and gender.
- Region of residence (North, Central, South).

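### The source named for time to chemotherapy in Section 8.3 contradicts Section 8.6, which says that source lacks chemotherapy such as cisplatin or carboplatin

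*Combined protocol and SAP*

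**What the plan says.** The Section 8.3 table lists time to chemotherapy after palbociclib as a reported clinical outcome. Its Source cell gives MHS structured data and nothing else. The definition is "Time to chemotherapy (Kaplan Meier method median (95% CI)) from end of index treatment and start of chemotherapy", and the planned summary is "Summary of number of events and censored patients at 6, 12, 18, 24 months".

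Section 8.6 divides the data by where they are held. The main database supplies "systemic therapy (not including chemotherapy like cisplatin or carboplatin". A second list, of items not available there, includes "chemotherapy (cisplatin, carboplatin), response (from imaging results"; these items "will be extracted through additional chart review from medical letters in PDF format by trained data extractors".

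Four places point to the use of both sources:

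- Section 8.1 has the database review followed by a medical record review, which together capture "clinical outcomes and post-palbociclib combination therapy treatment data".
- The sentence that introduces the Section 8.3 table reads "The following variables will be collected from the MHS electronic database and non-structured data extracted from PDF files of patient data".
- The lines-of-therapy row in that table gives its source as "MHS structured data and PDF patient data files".
- Section 8.3.3 builds treatment lines from the pharmacy database and from hospital records, the latter covering drugs obtained through private insurance or clinical studies.

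The visible text of Section 8.7 censors patients at the end of the study or when they leave MHS. Text beside that rule is redacted.

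**The concern.** The start of chemotherapy is the event that defines this outcome. The row assigns it to a source that, by the plan's own account, does not hold all chemotherapy. An analyst who works from the row would treat a patient whose chemotherapy appears only in a letter as still free of chemotherapy, and would carry that patient forward to a later visible start or to censoring. Chemotherapy would then seem to begin later after palbociclib than it did. An analyst who works from Sections 8.3.3 and 8.6 would count the same start as an event. The two could report different medians and different counts of events and censored patients at 6, 12, 18 and 24 months from the same records.

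**Working it through.** The plan gives no expected median, event count or capture rate for this outcome, so there is no figure to reproduce. The check is a comparison of the sections, followed by an argument for direction.

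1. **Is MHS structured data the same thing as the main database of Section 8.6?** Yes. Section 8.7 describes the study data as two parts, structured data from the MHS electronic database and non-structured data taken from PDF files. Section 8.6 makes the same division. The row's entry therefore cannot be read as already including the charts.

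2. **Does the Source column distinguish between sources?** Yes. Histology and ECOG status are assigned to the PDF files alone, lines of therapy to both sources, and time to chemotherapy to structured data alone. Against that contrast, a single entry reads as a rule.

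3. **Does another section override the row?** Not expressly. Sections 8.1, 8.3.3 and 8.6 and the lead-in to the table all suggest that both sources are intended. None of them says that time to chemotherapy is derived from the chart-supplemented lines.

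4. **Direction if the row is followed.** Let T be the true time from the end of palbociclib to the first chemotherapy, and T* the time visible in structured data. A start that is not visible can only be replaced by a later visible start or by none, so T* ≥ T for every patient and P(T* > t) ≥ P(T > t) at every t. With independent censoring, the Kaplan-Meier curve estimates P(T* > t), which lies on or above the curve that is wanted. For a start that never becomes visible, this can be seen in the calculation itself. With n patients at risk, the factor 1 − 1/n at that time becomes 1. The patient then stays in the risk set until censored, so later factors 1 − d/n become 1 − d/(n + 1), which are no smaller. The curve is raised from that point on.

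5. **Size.** Let f be the share of chemotherapy starts seen only in charts, and F(t) the true cumulative proportion with chemotherapy by time t. If f is unrelated to timing and hidden starts are never followed by a visible one, the curve reads (1 − f) × F(t). If some are followed by a visible one, it reads between (1 − f) × F(t) and F(t). The documents give neither f nor F(t). If chart data are used and are complete, f = 0 and the reading is F(t). Nothing in the documents bounds f from above: Section 8.6 describes the absent agents once with an open-ended phrase (see "systemic therapy (not including chemotherapy like cisplatin or carboplatin") and once with what may be a closed list (see "chemotherapy (cisplatin, carboplatin), response (from imaging results").

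**The case against.** The strongest reply is that the plan already deals with this. Section 8.6 supplies its own remedy by sending extractors to the letters for chemotherapy, and Sections 8.1 and 8.3.3 bring medical records into post-palbociclib treatment. Bias would require a team to extract chemotherapy from charts and then leave it out of the one outcome that chemotherapy defines. The study is also descriptive, with no comparator.

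Most of that stands. The likely intent is to use both sources, and the bias is conditional on a literal reading of the row. It does not remove the contradiction. The lead-in covers the whole table and cannot settle a row whose own cell is more specific, and Section 8.3.3 is not linked to this outcome. Section 8.4 describes the pharmacy records as full, but Section 8.6 makes a specific exclusion, which a general description does not cancel.

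A reader might infer more than the documents support:

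- *That post-palbociclib chemotherapy is not collected.* Section 8.6 says it is.
- *That all chemotherapy is absent from the main database.* The wording does not establish which agents are affected.
- *That time to next treatment has the same fault.* Its Source cell is the same, but it is defined by the date of the next line, and lines are identified from both sources.
- *That charts stop before the extended follow-up does.* Section 8.1 says treatment lines are rerun to 30 June 2022, and Section 5 gives that one date for the end of data collection. Neither says whether chart extraction runs to it, so this is a question and not a finding of bias.

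**Conclusion.** The contradiction in the stated source is established by the text. The plan collects the data needed, so this is not a gap in data collection. If the row is followed as written, starts seen only in charts are lost as events and the Kaplan-Meier time to chemotherapy is biased long. If both sources are used, this bias goes away to the extent that the charts are complete.

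The direction rests on two things: that an unseen start is replaced only by a later start or by censoring, and that the redacted text in Section 8.7 does not change the visible censoring rule in a way that matters here. The size cannot be estimated from the documents. A shift in months, or a statement that it exceeds sampling error, would need the share of chart-only starts, the true time distribution, and the follow-up available from the end of palbociclib. None of these is given. The point is a small correction that should be made before the analysis is run, because it decides which events count in a reported outcome.

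**What to change.** In the Section 8.3 table, change the source for time to chemotherapy to "MHS structured data and PDF patient data files", as in the lines-of-therapy row. Add a sentence that the chemotherapy start date is the earliest start after the end of index treatment found in either source, using the chart-supplemented treatment lines of Section 8.3.3.

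As a clarification only, state whether chart extraction also runs to 30 June 2022.

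The cost is one table cell and one or two sentences. No new data collection is needed, because Section 8.6 already has the chart data extracted.

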8.6.1. Case report forms (CRFs)/Data collection tools (DCTs)/Electronic data record

As used in this protocol, the term CRF should be understood to refer to either a paper form or an electronic data record or both, depending on the data collection method used in this study.

A CRF is required and should be completed for each included patient. The completed original CRFs are the sole property of Pfizer and should not be made available in any form to third parties, except for authorized representatives of Pfizer or appropriate regulatory authorities, without written permission from Pfizer. MHS shall ensure that the CRFs are securely stored at Maccabi Research & Innovation Institute in encrypted electronic and/or paper form and will be password protected or secured in a locked room to prevent access by unauthorized third parties.

MHS has ultimate responsibility for the collection and reporting of all clinical, safety, and laboratory data entered on the CRFs and any other data collection forms (source documents) and ensuring that they are accurate, authentic/original, attributable, complete, consistent, legible, timely (contemporaneous), enduring, and available when required. The CRFs must be signed MHS or by an authorized staff member to attest that the data contained on the CRFs are true. Any corrections to entries made in the CRFs or source documents must be dated, initialed, and explained (if necessary) and should not obscure the original entry.

The source documents are the hospital or the physician's chart. In these cases, data collected on the CRFs must match those charts.

8.6.2. Record retention

To enable evaluations and/or inspections/audits from regulatory authorities or Pfizer, MHS agrees to keep all study-related records, including the identity of all participating patients (sufficient information to link records, e.g., CRFs and physician records), copies of all CRFs, safety reporting forms, source documents, detailed records of treatment disposition, and adequate documentation of relevant correspondence (e.g., letters, meeting minutes, and telephone call reports). The records should be retained by MHS according to local regulations or as specified in the research agreement, whichever is longer. MHS must ensure that the records continue to be stored securely for so long as they are retained.

If MHS becomes unable for any reason to continue to retain study records for the required period, Pfizer should be prospectively notified. The study records must be transferred to a designee acceptable to Pfizer.

Study records must be kept for a minimum of 15 years after completion or discontinuation of the study, unless MHS and Pfizer have expressly agreed to a different period of retention via a separate written agreement. Record must be retained for longer than 15 years if required by applicable local regulations.

MHS must obtain Pfizer's written permission before disposing of any records, even if retention requirements have been met.

8.7. Data analysis

Data will consist of structured data from the MHS electronic database and non-structured data extracted from PDF files of patient data. Data validation will be performed and consist of quality control checks for appropriate values, logical sequences and quantity of missing values. Missing data will be identified and reported in the results tables as percentages for all variables. If there is a large amount of missing or illogical data, a decision to include, exclude or impute that variable will be subsequently made based on the study sponsor's decision.

Descriptive analyses will be conducted to evaluate the demographic, clinical and treatment characteristics overall, as well as for each of the study cohorts. Results will be reported in aggregate. Categorical variables (eg, ECOG performance status) will be reported as frequency and percentage. Continuous variables such as age will be reported as mean, (standard deviation) and median (Inter quartile range). In the case of missing observations, the number and percentage of missing values will be reported. Chi-square testing will be used to assess associations between categorical variables when patient counts for single cells within the results tables are greater or equal to 5. When distribution cannot be assumed to be Chi-square, then Fisher's exact test will be used. Depending on normality, analysis of variance (ANOVA)/t-tests or Kruskall-Wallis tests will be used for continuous variables. An alpha level of 0.05 will be the primary criterion for statistical significance of this study.

Time from treatment initiation until progression (as determined in the patient record) and drug discontinuation will be determined for the calculation of median time on treatment.

Duration of treatment on palbociclib, Time on treatment for subsequent line of therapy and Time to chemotherapy after palbociclib treatment and **CCI**

Plots will be generated. Patients are censored at end of study or left MHS.

Sub- analyses will be carried out for palbociclib.

All analyses will be conducted using IBM SPSS Statistics for Windows, Version 22.0. Armonk, NY: IBM Corp, and a P value < 0.05 is considered statistically significant.

8.8. Quality control

Quality control checks on MHS data are built into the "Clicks" physician visit management system and further quality control is carried out by the BI department.

8.9. Strength and limitations of the research methods

In general the study will be prone to selection bias and misclassification errors due to its observational design. Another potential limitation of the study could be the level of missing data. The possibility of selection bias is minimized because the study aims to include all metastatic breast cancer patients treated at MHS during a specified time period. In order to minimize the bias due to secondary data extraction from existing medical records, appropriate quality checks will be done by the analytical team. These checks include, but are not limited to, examination of missing and out of range values, comparison of data estimates to established norms, use of appropriate statistical methods to counteract the bias, wherever possible. Data cleaning procedures will be implemented

and updated at each data export and a review of clinical charts will be planned. A uniform handling of data that is conflicting, ambiguous, missing, or unknown will be performed. No statistical imputation of missing data is planned.

The study population and practice patterns captured in this study are from one health care provider and may not be representative of the country's breast cancer patient population and treatment practices. Therefore, the generalizability of the results may be limited. Small number of patients in certain stratification groups may result in wide CIs for estimates generated during the analyses.

ECOG performance status, which is likely predictive of anti-cancer treatment and CCI

Due to the descriptive nature of the study no inferences regarding causality can be drawn from the results.

